8.2. Exclusion Criteria

Patients are excluded from the study if any of the following criteria apply:

1. Therapy-resistant psoriasis defined as ≥2 treatment failures due to inadequate efficacy within the past 5 years of any biologic therapies (including but not limited to etanercept,

adalimumab, infliximab, certolizumab pegol, guselkumab, secukinumab, risankizumab, ixekizumab, tildrakizumab, or ustekinumab) administered in adequate dose and duration according to the label or local/national guidelines (patients who stopped systemic treatment for reasons not related to lack of efficacy are not excluded).

- 2. Unstable psoriasis or PsA with acute deterioration within 4 weeks of the Screening visit.
- 3. History of allergy or hypersensitivity to any component of the study treatment.
- 4. Active infection (eg, bacteria, viral, fungal) requiring treatment with systemic antibiotics within 4 weeks of the Screening visit.
- 5. Malignancy or history of malignancy except for treated (ie, cured) basal cell skin carcinomas.
- 6. Current diagnosis of predominant guttate, erythrodermic, exfoliative, or pustular psoriasis, or of drug-induced psoriasis, or other skin conditions that might confound the evaluation of psoriasis vulgaris, as judged by the Investigator (eg, AD, lupus).
- 7. Any recurrent medical condition associated with serious GI diseases, such as inflammatory bowel disease.
- 8. Any medical or psychiatric condition (eg, current major depression with a score for depressive symptoms ≥15 of HADS at Baseline, schizophrenia, suicidal behavior, psychiatric hospitalization within the prior year) which, in the Investigator's opinion, would preclude the patient from adhering to the protocol, completing the study per protocol, and/or would place the patient at unacceptable risk for receiving the investigational therapy.
- 9. Any therapies and systemic treatments as described in Table 3 which do not comply with the indicated washout interval.
- 10. Any previous treatment with orismilast or failure of treatment with apremilast or any other systemic PDE4 inhibitor as described in Table 3.
- 11. Any condition, including laboratory or ECG abnormalities, that places the patient at unacceptable risk to participate in the study or confounds the ability to interpret data from the study.
- 12. Severe hepatic impairment based upon medical history and laboratory abnormalities (eg, low albumin and abnormal bilirubin).
- 13. Any of the following abnormalities in clinical laboratory tests at Screening, as assessed by the study-specific laboratory and confirmed by a single repeat, if deemed necessary:
 - a. Absolute neutrophil count of $<3.0 \times 10^9/L$ ($<3000/mm^3$)
 - b. Hemoglobin of <10.0 g/dL or hematocrit <30%
 - c. Platelet count of $<100 \times 10^3$ cells/mm³ (SI: $<100 \times 10^9$ cells/L).
 - d. Absolute lymphocyte count of $<1.0 \times 10^9/L$ ($<1000/mm^3$)

- e. Total bilirubin >1.5 × the upper limit of normal (ULN); patients with a history of Gilbert's syndrome may have a direct bilirubin measured and would be eligible for this study provided the direct bilirubin is ≤ULN
- f. Alanine aminotransferase or aspartate aminotransferase $>2.5 \times$ the ULN.
- g. Serum creatinine ≥1.5 mg/dL. For a patient with a value of ≥1.5 mg/dL, a creatinine clearance of ≥60 mL/min (calculated using the CKD-EPI Creatinine Equation) is allowed.
- 14. History or evidence of hepatitis B virus (HBV) infection at Screening. Patients with positive hepatitis B surface antigen (HBsAg) are excluded. For patients with isolated positive antihepatitis B core antibody (HBcAb), hepatitis B surface antibody (HBsAb) result must also be positive to be considered for this study.
- 15. History or positive test result for hepatitis C virus (HCV) antibody, indicating ongoing infection, at Screening. Confirmatory testing for HCV RNA will be conducted for patients who have a positive test result. Patients who have a negative result for HCV RNA will be eligible to participate in the study.
- 16. History of positive HIV, or have congenital or acquired immunodeficiency (eg, common variable immunodeficiency disease). Patients who are positive for HIV antibodies (HIV-1 or HIV-2) at Screening are excluded from the study.
- 17. Suicidal ideation or behavior in the past 12 months as indicated by a positive response (yes) to questions 4 or 5 on the C-SSRS completed at the Screening visit or the C-SSRS completed at the Baseline visit.
- 18. Pregnant or breastfeeding.
- 19. History of alcohol or substance abuse within 6 months before Baseline that, in the opinion of the Investigator, will preclude participation in the study.
- 20. Institutionalized by court order or by local authority.

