	 b. Hemoglobin of <10.0 g/dL or hematocrit <30% c. Platelet count of <100 × 10³ cells/mm³ (SI: <100 × 10° cells/L). d. Absolute lymphocyte count of <1.0 × 10°/L (<1000/mm³) e. Total bilirubin >1.5 × the upper limit of normal (ULN); patients with a history of Gilbert's syndrome may have a direct bilirubin measured and would be eligible for this study provided the direct bilirubin is ≤ULN; f. Alanine aminotransferase or aspartate aminotransferase >2.5 × the ULN; g. Serum creatinine ≥1.5 mg/dL. For a patient with a value of ≥1.5 mg/dL, a creatinine clearance of ≥60 mL/min (calculated using the CKD-EPI Creatinine Equation) is allowed. 14. History or evidence of hepatitis B virus (HBV) infection at Screening. Patients with positive hepatitis B surface antigen (HBsAg) are excluded. For patients with isolated positive antihepatitis B core antibody (HBcAb), hepatitis B surface antibody (HBsAb) result must also be positive to be considered for this study. 15. History or positive test result for hepatitis C virus (HCV) antibody, indicating ongoing infection, at Screening. Confirmatory testing for HCV RNA will be conducted for patients who have a positive test result. Patients who have a negative result for HCV RNA will be eligible to participate in the study. 16. History of positive HIV, or have congenital or acquired immunodeficiency (eg, common variable immunodeficiency disease). Patients who are positive for HIV antibodies (HIV-1 or HIV-2) at Screening are excluded from the study. 17. Suicidal ideation or behavior in the past 12 months as indicated by a positive response (yes) to questions 4 or 5 on the C-SSRS completed at the Screening visit or the C-SSRS completed at the Baseline visit. 18. Pregnant or breastfeeding. 19. History of alcohol or substance abuse within 6 months before Baseline that, in the opinion of the Investigator, will preclude participation in the study.
Planned Sample Size:	20. Institutionalized by court order or by local authority. Approximately 200 patients will be enrolled to ensure approximately
	50 patients per arm. This sample size is based on assumptions that the percentage change from Baseline in PASI is -32.2% and -50.9% for placebo and each orismilast dose group, respectively, and the standard deviation is 33%. Using a 2-sided 2-sample t -test, 50 patients in each treatment arm can achieve a power of 80% at the significance level of 5%.
Investigational Therapy:	Name: orismilast

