12.8. The Columbia-Suicide Severity Rating Scale

The C-SSRS, Investigator administered version, was designed to provide a prospective, standardized measure of suicidality. The scale allows clinicians and researchers alike to assess the severity and lethality of suicidal behaviors and ideations and can be used to monitor treatment outcomes and establish suicide risk in a variety of research and clinical settings. Requiring approximately 5 min for completion, the C-SSRS is administered in the form of a clinical interview.

This C-SSRS is available in 2 versions: 1 for use at Screening referring to the past year and 1 for use throughout the rest of the study referring to the time since the prior visit.

If at Screening or Baseline there are "yes" answers on items 4 or 5 in the past year, the patient will not be included in the study.

Any subject with a positive response on the C-SSRS (answers "yes" to questions 1-5) should be referred to a mental health specialist (psychiatrist or clinical psychologist) for further evaluation, and the study medication should be paused. After a mental health specialist evaluation, the final decision on restarting or permanently discontinuing study treatment will be at the discretion of the Investigator in consultation with the mental health specialist. These cases should be reported as an AESI. Refer to Section 0.

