#### 4.2.2. Exclusion Criteria

Patients are excluded from the study if any of the following criteria apply:

1. Therapy-resistant psoriasis defined as  $\geq 2$  treatment failures due to inadequate efficacy within the past 5 years of any biologic therapies (including but not limited to etanercept, adalimumab, infliximab, certolizumab pegol, guselkumab, secukinumab, risankizumab, ixekizumab, tildrakizumab, or ustekinumab) administered in adequate dose and duration according to the label or local/national guidelines (patients who stopped systemic treatment for reasons not related to lack of efficacy are not excluded).
2. Unstable psoriasis or PsA with acute deterioration within 4 weeks of the Screening visit.
3. History of allergy or hypersensitivity to any component of the study treatment.
4. Active infection (eg, bacteria, viral, fungal) requiring treatment with systemic antibiotics within 4 weeks of the Screening visit.
5. Malignancy or history of malignancy except for treated (ie, cured) basal cell skin carcinomas.
6. Current diagnosis of predominant guttate, erythrodermic, exfoliative, or pustular psoriasis, or of drug-induced psoriasis, or other skin conditions that might confound the evaluation of psoriasis vulgaris, as judged by the Investigator (eg, atopic dermatitis, lupus).
7. Any recurrent medical condition associated with serious GI diseases, such as inflammatory bowel disease.
8. Any medical or psychiatric condition (eg, current major depression with a score for depressive symptoms  $\geq 15$  of HADS at Baseline, schizophrenia, suicidal behavior, psychiatric hospitalization within the prior year) which, in the Investigator's opinion, would preclude the patient from adhering to the protocol, completing the study per protocol, and/or would place the patient at unacceptable risk for receiving the investigational therapy.
9. Any therapies and systemic treatments as described in Protocol Section 9.5.2 which do not comply with the indicated washout interval. [REDACTED].
10. Any previous treatment with orismilast or failure of treatment with apremilast or any other systemic PDE4 inhibitor as described in Protocol Section 9.5.2.
11. Any condition, including laboratory or ECG abnormalities, that places the patient at an unacceptable risk to participate in the study or confounds the ability to interpret data from the study.
12. Severe hepatic impairment based upon medical history and laboratory abnormalities (eg, low albumin and abnormal bilirubin).

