13. Any of the following abnormalities in clinical laboratory tests at Screening, as assessed by the study-specific laboratory and confirmed by a single repeat, if deemed necessary:
  - a. Absolute neutrophil count of  $<3.0 \times 10^9/L$  ( $<3000/\text{mm}^3$ )

This document is confidential.

- b. Hemoglobin of <10.0 g /dL or hematocrit <30%
  - c. Platelet count of <100 × 10^3 cells/mm^3 (SI: <100 × 10^9 cells/L).
  - d. Absolute lymphocyte count of <1.0 × 10^9/L (<1000/mm^3)
  - e. Total bilirubin >1.5 × the upper limit of normal (ULN); patients with a history of Gilbert's syndrome may have a direct bilirubin measured and would be eligible for this study provided the direct bilirubin is ≤ULN
  - f. Alanine aminotransferase or aspartate aminotransferase >2.5 × the ULN;
  - g. Serum creatinine ≥1.5 mg/dL. For a patient with a value of ≥1.5 mg/dL, a creatinine clearance of ≥60 mL/min (calculated using the CKD-EPI Creatinine Equation) is allowed.
14. History or evidence of hepatitis B virus (HBV) infection at Screening. Patients with positive hepatitis B surface antigen (HBsAg) are excluded. For patients with isolated positive antihepatitis B core antibody (HBcAb), hepatitis B surface antibody (HBsAb) result must also be positive to be considered for this study.
15. History or positive test result for hepatitis C virus (HCV) antibody, indicating ongoing infection, at Screening. Confirmatory testing for HCV RNA will be conducted for patients who have a positive test result. Patients who have a negative result for HCV RNA will be eligible to participate in the study.
16. History of positive HIV, or have congenital or acquired immunodeficiency (eg, common variable immunodeficiency disease). Patients who are positive for HIV antibodies (HIV-1 or HIV-2) at Screening are excluded from the study.
17. Suicidal ideation or behavior in the past 12 months as indicated by a positive response (yes) to questions 4 or 5 on the C-SSRS completed at the Screening visit or the C-SSRS completed at the Baseline visit.
18. Pregnant or breastfeeding.
19. History of alcohol or substance abuse within 6 months before Baseline that, in the opinion of the Investigator, will preclude participation in the study.
20. Institutionalized by court order or by local authority.

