#### **12.7. The Columbia-Suicide Severity Rating Scale**

The C-SSRS, investigator administered version, was designed to provide a prospective, standardized measure of suicidality. The scale allows clinicians and researchers alike to assess the severity and

*This document is confidential.*

lethality of suicidal behaviors and ideations and can be used to monitor treatment outcomes and establish suicide risk in a variety of research and clinical settings. Requiring approximately 5 min for completion, the C-SSRS is administered in the form of a clinical interview. This C-SSRS is available in 2 versions: 1 for use at screening referring to the past year and 1 for use throughout the rest of the study referring to the time since the prior visit.

C-SSRS will be collected at different time points as per the SoA in Protocol Section 10.

The C-SSRS categories have been re-ordered from the actual scale to facilitate the definitions of the endpoints, and to enable clarity in the presentation of the results: category 1 – Wish to be Dead, category 2 – Non-specific Active Suicidal Thoughts, category 3 – Active Suicidal Ideation with Any Methods (Not Plan) without Intent to Act, category 4 – Active Suicidal Ideation with Some Intent to Act, without Specific Plan, category 5 – Active Suicidal Ideation with Specific Plan and Intent, category 6 – Preparatory Acts or Behavior, category 7 – Aborted Attempt, category 8 – Interrupted Attempt, category 9 – Actual Attempt (non-fatal), category 10 – Completed Suicide.

Suicidal ideation is defined as a “yes” answer at any time during treatment to any one of the five suicidal ideation questions (Categories 1-5) on the C-SSRS. Suicidal behavior is defined as a “yes” answer at any time during treatment to any one of the five suicidal behavior questions (Categories 6-10) on the C-SSRS. Suicidal ideation or behavior is defined as a “yes” answer at any time during treatment to any one of the ten suicidal ideation and behavior questions (Categories 1-10) on the C-SSRS.

A summary table presenting number of patients with suicidal ideation, suicidal behavior, and self-injurious behavior without suicidal intent will be generated, as well as a shift table to demonstrate changes in C-SSRS suicidal ideation scores from baseline to all post-baseline visits by treatment. Patients with suicidal ideation, suicidal behavior, or self-injurious behavior without suicidal intent based on the C-SSRS will be listed.

This document is confidential.

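### Exclusion 17 claims to cover suicidal behaviour but is triggered only by two C-SSRS ideation questions, so a patient positive on behaviour alone is not automatically excluded

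*Protocol*

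**What the plan says.** Exclusion 17 in Protocol 8.2 reads "Suicidal ideation or behavior in the past 12 months as indicated by a positive response (yes) to questions 4 or 5 on the C-SSRS", as completed at Screening or Baseline. The synopsis has the same text ("Suicidal ideation or behavior in the past 12 months as indicated by a positive response (yes) to questions 4 or 5"), and SAP 4.2.2 repeats the trigger ("positive response (yes) to questions 4 or 5 on the C-SSRS"). The entry rule in Protocol 12.8 matches: given yes "answers on items 4 or 5 in the past year, the patient will not be included in the study".

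Suicidal behaviour appears in one other entry criterion. Exclusion 8 lists it as an example of a psychiatric condition: "schizophrenia, suicidal behavior, psychiatric hospitalization within the prior year) which, in the Investigator's opinion, would preclude the patient from adhering to the protocol", or would prevent completion or create unacceptable risk. SAP 4.2.2 gives the same list ("schizophrenia, suicidal behavior, psychiatric hospitalization within the prior year"). Exclusion 11 is a general clause for any condition "that places the patient at unacceptable risk to participate in the study".

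On study, Protocol 12.8 says that a yes to any of questions 1 to 5 should lead to specialist referral and a pause of study drug. Protocol 12.9.2 lists both suicidal ideation and suicidal behaviour as events of special interest.

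**The concern.** The criterion names two things, ideation and behaviour, but its indicator measures only the first. Read literally, the words on behaviour have no effect.

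This matters because Protocol 5.3 treats depression and suicidal thoughts as a potential effect of the drug class and states that people at risk of suicide will be kept out. As written, ideation with intent leads to automatic exclusion, while a reported attempt or preparatory act without that ideation does not. The decision for such a patient passes to individual judgement and may differ between sites.

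**Working it through.** There is no figure to reproduce. The check compares the trigger with the content of the form.

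**Step 1: what questions 4 and 5 measure.** On the sample Screening form (Protocol Appendix 10), question 4 asks about intention to act on suicidal thoughts and question 5 about working out a plan. The form for later visits labels both items as active suicidal ideation. SAP 12.7 agrees independently: it defines ideation as a yes to "any one of the five suicidal ideation questions (Categories 1-5) on the C-SSRS", and behaviour as a yes in categories 6 to 10.

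**Step 2: where behaviour is asked.** On the sample Screening form it is question 6 only. On the form used from Baseline it is a separate section with four items: actual attempt, interrupted attempt, aborted or self-interrupted attempt, and preparatory acts. A further item on nonsuicidal self-injury is not counted as suicidal behaviour.

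**Step 3: count the items each rule uses.**

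| Form | Rule | Ideation items used | Behaviour items used |
|---|---|---|---|
| Sample Screening form | Exclusion 17 and 12.8 entry rule | 2 of 5 | 0 of 1 |
| Form from Baseline on | Exclusion 17 and 12.8 entry rule | 2 of 5 | 0 of 4 |
| Form from Baseline on | 12.8 referral and pause rule | 5 of 5 | 0 of 4 |

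**Step 4: follow one patient through.** Take a patient with a suicide attempt eight months before Screening who answers no to question 2. The sample Screening form then skips questions 3 to 5 and goes to question 6, which is answered yes. Questions 4 and 5 were never asked, so neither Exclusion 17 nor the 12.8 entry rule applies. Only Exclusion 8 or 11 can keep this patient out. Protocol Section 18 says the appended forms are samples, so the skip may differ in practice. The gap does not depend on it: a patient who is asked questions 4 and 5, answers no to both, and reports behaviour also passes Exclusion 17.

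**Step 5: compare with how the protocol treats depression.** A HADS depression score of 15 or more is also only an example within Exclusion 8, but Protocol 12.7 adds an unconditional bar to randomization at that score. Suicidal behaviour has no such bar.

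**Step 6: on study.** The form defines an actual attempt as involving some wish to die, so an attempt would usually also give a yes to question 1 and reach the pause rule. An attempt may also be Grade 3 or worse (permanent discontinuation, Protocol 9.3) or a serious event (12.9.3). The remaining cases are mainly preparatory, aborted or interrupted acts, or attempts where intent is denied but inferred, with questions 1 to 5 all no and a grade below 3.

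**The case against.** The strongest reply is that entry is already handled in practice. Exclusion 8 names suicidal behaviour. Exclusion 11 covers unacceptable risk and does not contain the words on investigator opinion. Protocol 5.3 gives investigators a clear direction. The C-SSRS is an interview conducted by the investigator, so the person who hears of the behaviour also applies those exclusions. The 12.8 referral sentence is not expressly limited to visits after Baseline, so a patient with a yes to question 1, 2 or 3 might be referred before entry. Finally, the indicator phrase in Exclusion 17 can be read as limiting the criterion to what questions 4 and 5 capture, which would make the mention of behaviour loose drafting.

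Much of this stands as mitigation. Behaviour is not ignored at entry, and the remaining risk is an investigator who knows of recent behaviour and still accepts the patient. But Exclusions 8 and 11 both require someone to judge the risk, 5.3 states an intention without an operating rule, and referral is not exclusion. If the mention of behaviour is loose drafting, the text still needs correcting, and deleting it would move the criterion further from 5.3.

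The on-study point is fairly called an omission and is narrow. The remaining cases still get 24-hour reporting as events of special interest, Protocol 8.4 permits withdrawal, and the existing pause rule itself says should. It is secondary to the entry criterion.

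**Conclusion.** The concern holds. As written, Exclusion 17 and the 12.8 entry rule do not exclude a patient who is positive on suicidal behaviour alone, although Exclusion 17 says that it covers behaviour. The conclusion rests on the classification of questions 4 and 5 as ideation, on which Appendix 10 and SAP 12.7 agree, and not on the skip in the sample form.

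The item counts describe the gap in the rule; they do not measure risk. The documents give no expected number of behaviour-only positives. My assumption is that there would be very few, because behaviour usually comes with ideation. Sample size, power and the efficacy analyses are unaffected. The point should be corrected because a rare failure could be serious and the correction is cheap.

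**What to change.** 1. **Entry.** In Exclusion 17 (synopsis, Protocol 8.2, SAP 4.2.2) and the 12.8 entry rule, add after questions 4 or 5: *or a yes to suicidal behaviour (actual, interrupted or aborted attempt, or preparatory acts; not nonsuicidal self-injury) within the past 12 months on the Screening or Baseline C-SSRS*. The SAP change only keeps the restated criteria aligned.
2. **Date.** Leave the C-SSRS unchanged and record the date of the most recent behaviour in the source and eCRF. Sample question 6 asks about any time in life and then only about the last 3 months, so it cannot by itself settle a 12-month window. At Baseline no date is needed to decide: the form covers the time since the prior visit, at most 28 days, so any yes falls within 12 months.
3. **On study (secondary).** Add the same four behaviour items to questions 1 to 5 in the 12.8 referral and pause rule.

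The cost is a wording change in the protocol and SAP, one date field, and possibly a very few additional exclusions or drug pauses.
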